## **Processing Technique**

### **Caudal Epidural Steroid Injection (CESI):**

CESI procedure, which is a treatment method applied in routine clinical practice in patients diagnosed with FBSS who do not respond to conservative treatments, will be performed by an algologist ([name]) with at least 10 years of experience in this field. During the procedure, the distance rule will be observed as much as possible (the person performing the procedure must be as close to the patient).

After patients are placed in the prone position, a pillow will be placed under the patient's abdomen to reduce lumbar lordosis. The injection site will be cleaned three times with povidone-iodine antiseptic and then covered with a sterile drape. In the operating room, patients will receive standard monitoring (ECG, MAP, SpO2) and vascular access will be established with a 20 G branule. Short-acting local anesthesia (3 mL 2% prilocaine) will be applied to the skin and subcutaneous tissue. A 3.5-inch, 22-gauge spinal needle will be inserted into the caudal epidural space, verifying that the needle does not exceed the level of the S3 foramen. 1- 2 mL contrast material (300 mg/50 ml iohexol) will be administered and the distribution of the injectate will be monitored simultaneously in Doppler mode, and the distribution pattern showing bilateral L5-S3 spread without vascular spread will be displayed. A mixture of 40 mg (1 mL) triamcinolone acetonide, 7 mL physiological saline and 2 mL (0.5%) bupivacaine will be injected, a total of 10 mL mixture will be used, all patients will be monitored and evaluated for one hour after the procedure. Patients without any procedural complications will be discharged.

## **Power analysis**

According to the study conducted by Sacaklı R. et al., based on the improvement in pain scores in the 3rd month, the number of samples was found to be 21 for the CS group and 25 for the non-CS group, with a 95% confidence interval and 90% power. Considering that 10% of the patients could not continue the study, a total of 51 patients were planned to be included.

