found to be effective and safe in treatment. CESI has been shown to be the safest and simplest ESI with a low rate of complications, including dural puncture and other side effects, compared to other injection methods (9). Yoon et al. (10) reported the success rate of US-guided caudal blockade as 94% (11). In a study conducted by Akkaya et al. (12), comparing ultrasound and fluoroscopy-guided caudal epidural steroid injection (CESI) in patients with FBSS, a decrease in both pain and ODI scores was achieved in both groups at 3-month follow-up, and CESI was found to be effective in the treatment of FBSS. has been reported. In a prospective randomized controlled study comparing the treatment success of caudal epidural steroid injection guided by ultrasonography (USG) and fluoroscopy in postlaminectomy patients, no difference was found in terms of complications between the two groups, while patients in the fluoroscopy group felt more pain during the intervention than patients in the USG group. Despite accurate needle localization and drug injection under fluoroscopic guidance, radiation is still a serious risk for both the patient and the interventionalist. The use of USG in caudal epidural injections protects against radiation exposure and is a safe and rapid method to locate the sacral hiatus and guide the needle (9). Color Doppler USG can visualize intravenous injections. Tsui et al. (13) reported that the color Doppler feature of US can confirm whether the injected drug diffuses into the caudal area. Injection of fluid into the epidural space causes turbulent flow, which appears as a burst of color, whereas intrathecal injection shows the absence of color flow Doppler signal. Although the exact pathophysiological process of FBSS remains unclear, increasing evidence suggests that the symptoms of diffuse pain distribution, hyperalgesia, and disproportionate pain intensity, which are also common in other chronic pain-related diseases (e.g., fibromyalgia, tension-type headache, and nonspecific chronic low back pain), are a potential pain disorder. predicts that central sensitization may develop (14). The International Association for the Study of Pain (IASP) defined CS in 2011 as "the increased response of nociceptive neurons in the central nervous system to normal or subthreshold afferent input." Anxiety about pain, limitation of daily activities, quality of life and related stress lead to depression over time, thus beginning a vicious "pain-anxiety-depression" cycle. Altered central pain modulation may be involved in the pathogenesis of FBSS. Unfortunately, only a few studies have investigated the presence of central sensitization in patients with FBSS, although it may guide treatment. Central amplification of pain may contribute to both chronic low back pain intensity and disability in FBSS patients. Therefore, targeted treatments should take into account functional changes in the central nervous system of FBSS patients, and treatment modalities that can attenuate central sensitization (e.g., cognitive targeted exercise therapy, pharmacotherapy, spinal cord stimulation) may be useful in the treatment of FBSS. Our aim is to reveal the relationship between FBSS and central sensitization proportionally, to prevent the formation of a vicious circle of chronic pain with early detection and treatment, keeping in mind that central sensitization may develop in postspinal surgery patients with ongoing pain, and also to prevent the formation of a vicious cycle of chronic pain with USG-guided caudal epidural steroid injection, as there is no radiation exposure and it is advantageous and beneficial. Since it is a reliable

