## **10-APPROACHES AND METHODS TO BE APPLIED :**

Among the patients who applied to Marmara University Pendik Training and Research Hospital, Physical Medicine and Rehabilitation and Algology outpatient clinics with complaints of low back pain, were diagnosed with FBSS by Algology after clinical, physical examination and radiological imaging and were planned for caudal epidural steroid injection, which is a treatment option applied in routine clinical practice. Those who meet the exclusion criteria will be included in the study after detailed information about the research is given and their verbal and written consent is obtained. These patients will not undergo additional treatment, any imaging methods or laboratory tests. Patients diagnosed with or in contact with Covid-19 will not be processed until the quarantine period expires. Patients will be reminded to comply with the mask and distance rules in the waiting area before the procedure and in the observation area after the procedure, not to touch any surfaces in the hospital unless necessary, and to frequently disinfect their hands. During the evaluations, the patient and the physician; will comply with mask, distance and hand hygiene rules. After the procedure, a waiting area will be allocated for patients in accordance with distance rules.

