Patients who meet the Chronic Low Back and Leg Pain consensus group FBSS definition and meet the inclusion criteria will be included in the study. Before the patients are processed, data such as demographics, height, weight, which leg the pain is on, additional diseases, and medications used will be recorded. Before the procedure, patients will be evaluated with scales and methods such as Numeric Rating Scale (NRS), Oswestry Disability Index (ODI), Central Sensitization Inventory (CSI), Beck Depression Inventory (BDI), Douleur Neuropathic 4 (DN4) and a pressure algometer (baseline brand manual Quantitative sensory testing will be performed using algometer) . Those who score 40 and above on CSI will be included in Group 1 (those with CS), and those with lower scores will be included in Group 2 (those without CS). Homogeneity between groups will be ensured in terms of the surgical method applied (lumbar stabilization or microdiscectomy) and etiological cause (fibrosis and recurrent disc herniation). Patients in both groups will undergo CESI under USG guidance. Patients will be re-evaluated with NRS at 1 hour, 3 weeks and 3 months after the procedure, using the scales and methods mentioned above. A 50% or more reduction in NRS in the 3rd month will be considered treatment success.

Numeric Rating Scale (NRS) is a scale in which the patient gives a score between "0" and "10" for the back and leg pain felt, where "0" = no pain and "10" = the most severe, unbearable pain. is a scale. Turkish validity and reliability studies of the scales and surveys to be used in the study have been conducted and are stated in the references.

The Central Sensitization Inventory (CSI) includes 2 parts: part A, which evaluates symptoms thought to be related to CS, and part B, which quickly questions whether the patient has previously received a specific diagnosis. Part A contains 25 items that question the frequency of symptoms seen in SS syndromes and are scored between 0-100 points. Each symptom is defined as "never" (0 points) if the patient never experiences that symptom, "rarely" (1 point) if the patient experiences it rarely, "sometimes" (2 points) if he sometimes experiences it, "often" (3 points) if he frequently experiences it, "frequently" (3 points) if he always experiences it. It is recorded as "always" (4 points). As the patient's score increases, he or she is considered to have more symptoms related to CS.

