#### **D-OTHER INFORMATION ABOUT VOLUNTEERS**

Minimum number of volunteers to be included in the study	Total	Age range
Group-1 CS ones	24	18-75
Group-2 non-CS	27	18-75

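### Does a planned total of 51 that equals the sum of the two group minima (24 + 27) force quota recruitment and spoil an estimate of the CS proportion?

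*Protocol*

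**What the plan says.** The Protocol's Power analysis gives the evaluable sizes: "the number of samples was found to be 21 for the CS group and 25 for the non-CS group", at 90% power and 95% confidence. It then adds the allowance for loss: "Considering that 10% of the patients could not continue the study, a total of 51 patients were planned to be included".

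Section D (other information about volunteers) heads its table "Minimum number of volunteers to be included in the study" and lists 24 for the CS group and 27 for the non-CS group.

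Section 10 (approaches and methods) forms the groups from the CSI score taken before the procedure: "Those who score 40 and above on CSI will be included in Group 1 (those with CS"; lower scores go to Group 2. It draws patients from those who "were planned for caudal epidural steroid injection" in routine care.

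Section 9 (justification and purpose) contains the phrase that raises the question of a proportion: "Our aim is to reveal the relationship between FBSS and central sensitization proportionally".

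**The concern.** Three statements seem to pull against each other. The total is 51, the two minima add up to 51, and group membership is observed and cannot be assigned. If 51 is a fixed total, both minima are met only when exactly 24 of the 51 patients score 40 or more. Unselected recruitment would rarely produce that, so the figures appear to imply that patients are accepted or refused by CSI score until each group is full.

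In that case the enrolled CS share would be 24/51 = 47% by design and would say nothing about how common CS is in failed back surgery syndrome (FBSS). If the purpose statement in section 9 means prevalence, that aim would be lost. It could not be recovered later if patients had been turned away without their scores being kept.

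**Working it through.** **Inputs.** From the Power analysis: 21 and 25 evaluable patients (46 in all), 90% power, 95% confidence, 10% loss, total 51. From section D: minima of 24 and 27. From section 10: CSI cut-off 40. Not in the Protocol: the true CS share p (assumed 30-60%), the effect size, the test and its sidedness.

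**Step 1. The planned total.** 46 × 1.10 = 50.6, rounded up to 51. Alternatively 46 / 0.90 = 51.1, which is 51 to the nearest whole patient. The total reproduces. By group, 21 / 0.90 = 23.3, rounded up to 24; 25 / 0.90 = 27.8, against 27 stated, a difference of one patient after rounding up. The sum is 24 + 27 = 51.

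**Step 2. Chance of an exact 24/27 split.** With 51 unselected patients this is C(51,24) · p^24 · (1 − p)^27, which is largest at p = 24/51.

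**Step 3. Total needed if both minima bind and 51 may be exceeded.** With N the number recruited when both minima are first met and X the number with CS among n, P(N ≤ n) = P(24 ≤ X ≤ n − 27). The mean of N follows from summing 1 − P(N ≤ n) over n.

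**Step 4. Power if 51 consecutive patients are taken as they come.** Assume a two-sided t-test at 0.05. Solving for 90% power at 21/25 gives a standardised difference of 0.981. Completers are 51 × 0.90 = 45.9, taken as 46. Power is averaged over splits with X ~ Binomial(46, p). It falls below 80% only when one group has 11 or fewer completers (11/35 gives 79.3%, 12/34 gives 81.5%).

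| Assumed CS share | Exact 24/27 split | Mean total to meet both minima | Average power, 51 consecutive | Chance that power is below 80% |
|---|---|---|---|---|
| 30% | 0.4% | 80 | 83.2% | 23.3% |
| 40% | 6.6% | 61 | 88.2% | 1.7% |
| 47% | 11.1% | 57 | 89.4% | 0.1% |
| 50% | 10.2% | 57 | 89.5% | 0.1% |
| 60% | 2.0% | 68 | 88.2% | 1.7% |

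**Step 5. What the text commits to.** The Power analysis gives a planned number; section D gives two lower bounds. Together they say that at least 51 patients are intended. They conflict only if 51 is also an upper bound, and nothing in the Protocol makes it one; the word minimum points the other way. Section 10 places every included patient in one of two groups by score and describes neither a quota nor the closing of a group. The follow-up form in Annex II has a CSI row with a pre-procedure column, so the score is recorded for each enrolled patient.

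**Step 6. What the feared harm would need.** All of the following would have to be true: 51 is a ceiling; a group closes when full; patients are refused by CSI score without a record; the loose phrase in section 9 means prevalence; and 24/51 is then reported as that prevalence. None of the five is stated. The title, the grouping, the success definition (a reduction of at least 50% in the pain score at month 3) and the sample size all concern treatment response in CS versus non-CS patients.

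**The case for a change.** The strongest case for the concern is that the total, the minima and the aim are all fixed in the Protocol, so their fit and the end of recruitment are protocol matters, and a later analysis plan could not recover the scores of patients turned away. A sentence would cost little now. Section 10 also promises homogeneity between the groups in surgical method and cause without saying how. If that is done by choosing patients, enrolment is not consecutive and the binomial figures above no longer apply.

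Part of this stands. The arithmetic is right, the Protocol does not say when recruitment stops, and the homogeneity sentence is the only text that hints at selective recruitment. But that sentence concerns surgery and cause, not CSI score, and it sets no quota by group. The other points show that a rule is unwritten, not that a written rule is wrong. The denominator and interval for a descriptive proportion are commonly left to an analysis plan, which is not at hand here. The usual remedies, either exceeding 51 until both minima are met or taking 51 consecutive patients and accepting the split, trade recruitment length against power. Choosing between them is a preference and corrects no stated figure.

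**Conclusion.** The concern does not hold. The equality 24 + 27 = 51 is what one expects when the minima and the planned total come from the same sample size calculation, and the statements are compatible as written. The low chance of an exact 24/27 split, at most 11.1%, has little consequence because the group comparison does not require that split. With 51 consecutive patients, average power stays at 88-90% for a CS share of 40-60%, with at most a 1.7% chance of falling below 80%. The loss is visible only near a 30% share: 83% on average, with a 23% chance of falling below 80%.

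These figures rest on the assumed CS shares, unselected enrolment, 46 completers and a two-sided t-test with an effect back-solved from 21/25; the Protocol gives none of the shares, the test or the effect. The conclusion that nothing is contradicted rests on the text alone and does not depend on them. It would change if another document fixed 51 as a ceiling with groups closed by CSI score and reported the enrolled CS share as a prevalence.

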#### **D-OTHER INFORMATION ABOUT VOLUNTEERS**

Minimum number of volunteers to be included in the study	Total	Age range
Group-1 CS ones	24	18-75
Group-2 non-CS	27	18-75

#### **12- CRITERIA FOR INCLUSION, EXCLUSION AND REMOVAL FROM THE RESEARCH**

##### INCLUDING:

- Being between the ages of 18-75
- Those who meet FBSS diagnostic criteria (according to CBLP)
- Radicular pain that begins at any time after surgery and persists for at least 6 months
- Those with clinically compatible epidural fibrosis and/or disc herniation at the L5 and/or S1 vertebra level on contrast-enhanced MRI
- Nrs is greater than or equal to 4
- Failure to achieve significant improvement with conservative methods

- Volunteering to participate in the study and signing a consent form

**EXCLUSION:**

- Those with acute or chronic uncontrolled medical illness,
- Lumbar structural pathologies (e.g., traumatic spinal injuries, infections, tumor and ankylosing spondylitis)
- Those with isolated axial low back pain
- Those with a history of lumbar surgery other than lumbar stabilization or microdiscectomy
- History of adverse reactions to local anesthesia or steroids
- Being pregnant or breastfeeding
- History of allergy to the injectables to be administered
- Those with bleeding diathesis
- Mental, psychiatric or neurological diagnosis that may complicate the implementation of the study
- Not wanting to participate in the study

**ANNEX-II**

## PATIENT FOLLOW-UP FORM

**Name surname:**

**History:**

**Phone:**

**TC Identification number :**

**Age:**

**Address:**

**Gender:**

**Kilo:**

**Size:**

**BMI:**

**Marital status:**  Married  Single

**Occupation:**  Housewife  Student  Civil servant  Worker  Retired

**Educational status:**  Illiterate  Literate  Primary school  Middle school  High school

College  University

**Previous surgery;**

**The party to be transacted; Duration of symptoms: Comorbidity:**

Radicular pain; **Previous treatments / duration :** Medications used

	Before Procedur e	1st hour	Three weeks	3 months
NRS (Waist)				
NRS (Leg)				
CSI				
BDI				

ODI				
PPT				
DN4
